	Tower Building, University of Nottingham, [name]					
	[contact]					
	Email: [contact]					
Sponsor:	University Hospitals of Derby & Burton NHS Foundation Trust					
	Royal Derby Hospital, [name]					
	[contact]					
	Email: [contact]					
Funder(s):	NIHR Programme Grants for Applied Research					
	NIHR Central Commissioning Facility					
	Email: [contact]					
	[contact]					
Trial Manager	[name]					
	York Trials Unit					
	Department of Health Sciences, University of York					
	[name]					
	[contact]					
	Email: [contact]					
Clinical Trials Unit:	York Trials Unit					
	Department of Health Sciences, University of York, [name]					
	[contact]					
Statistician:	[name]					
	York Trials Unit					
	Department of Health Sciences, University of York, [name]					
	[contact]					
	Email: [contact]					
Health Economist	[name]					
	College of Human and Health Sciences, Room: SCHE – 218,					
	[name]					
	[name]					
	[contact]					
	Email: [contact]					

STUDY SUMMARY

Study Title:	Reducing the impact of diabetic foot ulcers: Pilot trial						
Short Title:	Reducing the impact of DFUs: Pilot trial						
Sponsor Reference:	UHDB/2020/037						
Study Design:	Multi-centre randomised controlled pilot trial with nested qualitative study						
Study Participants:	Pilot trial: People with diabetes, two lower limbs and a recently healed DFU (fully epithelialised with no drainage, for a minimum two weeks). Nested qualitative study: Intervention participants and healthcare professionals delivering REDUCE.						
Planned Number of Sites:	Two secondary care NHS Trusts will recruit patients and deliver the intervention. Follow up data will be collected from secondary care, primary care and community health including podiatry and wound care medical records.						
Planned Sample Size:	N=23, consisting of: 20 participants and three healthcare professionals						
Treatment Duration:	3 months						
Follow Up Duration:	4 months						
Planned Start Date:	19/04/2021						
Planned Recruitment End Date:	18/07/2021						
Planned Study End Date:	31/03/2022						
Research Question/ Aims:	 The primary objectives of this pilot trial are to investigate the following prior to conducting a larger clinical and cost-effectiveness trial: Feasibility of the recruitment strategy for participants, to include numbers of eligible patients approached, numbers not eligible (and why), and proportion of eligible patients consented. Adherence to and attrition from the REDUCE intervention and to the trial (to include reasons for attrition and how this is documented). Feasibility of obtaining outcome data from primary, community and secondary care patient medical records. Completeness of data collection. Feasibility of collecting the planned economic outcome measures. Completeness of data collected. Identify whether adaptations are required to the REDUCE intervention. Test out and refine data collection methods for the mixedmethods process evaluation to be undertaken in the main trial. Determine if refinements are required to the intervention fidelity tool. Determine if modifications are needed prior to the clinical and cost-effectiveness trial to:						

FUNDING AND SUPPORT IN KIND

Funder(s)	Financial and Non-Financial Support Given
NIHR PGfAR (Reference: RP-PG-0618-20001)	£2,531,202

ROLES & RESPONSIBILITIES

Sponsor

The Sponsor, University Hospitals of Derby & Burton NHS Foundation Trust, take on overall responsibility for appropriate arrangements being in place to set up, run and report the research project. The Sponsor is not providing funds for this study, but has taken on responsibility for ensuring finances are in place to support the research.

Funder

The study is funded by the National Institute for Health Research (NIHR) Programme Grants for Applied Research (PGfAR), reference RP-PG-0618-20001.

Study Management Committees

Trial Management Group (TMG)

The day to day running of the work described in this protocol will be overseen by the TMG which consists of all the applicants and collaborators involved in the pilot trial. This group will have face-to-face meetings every quarter and monthly teleconferences. Any problems with study conduct will be raised and addressed during TMG meetings.

Trial Steering Committee (TSC)

The TSC will oversee and supervise the progress of the trial and ensure that it is being conducted according to the protocol and the applicable regulations. The TSC is an independent body that includes members who are not involved with the running of the trial and will meet bi-annually during the pilot trial. The TSC consists of five members; an independent Chair with expertise in health psychology, an independent clinician with expertise in diabetes, an independent member with expertise in podiatry, an independent statistician and an independent patient and public involvement (PPI) representative. Representatives from the Trial Management Group will attend the TSC to provide the updates, to include Chief Investigator, Trial Manager, Trial Statistician and Programme Manager. Other members will be invited on an 'as required' basis. A Data Monitoring and Ethics Committee will not be convened for this pilot trial.

The Trial Steering Committee will also meet as the Independent Programme Steering Committee (IPSC). For IPSC meetings, a Sponsor representative and a Funder representative may also be in attendance. The IPSC will meet annually over the duration of the Programme.

Programme Management Group (PMG)

The study is part of a larger programme of work which will be overseen by the REDUCE PMG. The PMG consists of all the applicants and collaborators on the wider programme (including members of this TMG), and one lay/PPI member. The PMG will meet bi-annually over the programme to oversee

the management of all work packages (WPs), including the work described here. The PMG will be notified of any problems with study conduct. A representative from the sponsoring organisation and the University of Nottingham Technology Transfer Office will also attend these meetings, where able, to ensure any new intellectual property (IP) is captured in a timely fashion.

Protocol Contributors

A number of protocol contributors have been involved in the development of this protocol. These include the Chief Investigators, named Co-applicants and Collaborators, Programme Manager, Statistician, Data Manager, Trial Manager, Sponsor Representative, Patients and Carers.

Contents

SI	GNATURE	PAGE	2
ΚI	EY STUDY	CONTACTS	3
S٦	TUDY SUM	IMARY	6
Fι	JNDING A	ND SUPPORT IN KIND	7
R	OLES & RE	SPONSIBILITIES	7
LI	ST OF ABB	REVIATIONS	11
S٦	TUDY FLO	N CHART – PARTICIPANTS	13
S٦	TUDY PRO	TOCOL	
1.		BACKGROUND AND RATIONALE	15
	1.1.	The Revised REDUCE Intervention	16

	11.0.	Investigators at Each Site and Committee Members for the Overall Study Managemer	nt
	11.9.	Indemnity	
	11.10.	Amendments	
	11.11.	Access to Final Study Dataset	
	12.1.	Dissemination Policy	
	12.1.	Authorship Eligibility Guidelines and any Intended Use of Professional Writers	
13		REFERENCES	
14		APPENDICES	
1,	+. 14.1.	Appendix 1 – Schedule of Assessments: Participants	
	14.1.	Appendix 2 – Schedule of Assessments: Healthcare Professionals	
	14.2. 14.3.	Appendix 2 – Schedule of Assessments. Healthcare Professionals	
	±4.J.	Appendix 3 - Amendment History	40

LIST OF ABBREVIATIONS

AE Adverse Event

APR Annual Progress Report

B-IPQ Brief Illness Perception Questionnaire

CBRQ Cognitive and Behavioural Responses Questionnaire

CBT Cognitive Behavioural Therapy

Cl Chief Investigator

CONSORT Consolidated Standards of Reporting Trials

CRF Case Report Form

DDS Diabetes Distress Screening

DFU Diabetic Foot Ulcer
DMP Data Management Plan

GAD Generalised Anxiety Questionnaire

GCP Good Clinical Practice

GI Global Initiative

GP General Practice/Practitioner

HCP Healthcare Professional

HEAP Health Economic Analysis Plan HRA Health Research Authority

ICECAP-A ICEpop CAPability measure for Adults

ICF Informed Consent Form

ICH International Conference on Harmonisation of technical requirements for

registration of pharmaceuticals for human use

ICJME International Committee of Journal Medical Editors

IP Intellectual Property

IPAQ-E International Physical Activity Questionnaire - Elderly

IPSC Independent Programme Steering Committee

ISF Investigator Site File

ISRCTN International Standard Randomised Controlled Trials

KCL King's College London

MHC-SF Mental Health Continuum – Short Form

MI Maintenance Intervention MRC Medical Research Council

NAFF Nottingham Assessment of Functional Footcare

NHS R&D National Health Service Research & Development

NICE National Institute for Health and Care Excellence

NIHR National Institute for Health Research

PAD Peripheral Arterial Disease
PBA Person Based Approach

PGfAR Programme Grants for Applied Research

PHQ Patient Health Questionnaire

PI Principal Investigator

PIC Participant Identification Centre
PIS Participant Information Sheet

PMG Programme Management Group
PPI Patient and Public Involvement

QA Quality Assurance QC Quality Control

R&D Research and Development
RCT Randomised Controlled Trial
REC Research Ethics Committee
SAE Serious Adverse Event
SAP Statistical Analysis Plan
SDV Source Data Verification

SOP Standard Operating Procedure

SPANE Scale of Positive And Negative Experience

SPS Social Provisions Scale
TMG Trial Management Group
TSC Trial Steering Committee

[figure not shown]
TMF Trial Master File

UHDB University Hospitals of Derby and Burton NHS Foundation Trust

[figure not shown]
UK United Kingdom

UoE University of Edinburgh
UoN University of Nottingham
VAS Visual Analogue Scale
WHO World Health Organization

WP Work Package
YTU York Trials Unit

STUDY FLOW CHART - HEALTHCARE PROFESSIONALS

STUDY PROTOCOL

1. BACKGROUND AND RATIONALE

One in 15 people in the UK has diabetes [1]. Foot ulceration is a common, chronic and costly complication of the disease: affecting a quarter of patients [2]; 70% of ulcers remain unhealed after five months [3] and 80% of the 2,200 major amputations in patients with diabetes per-annum are preceded by foot ulcers [4]. The physical and emotional burden of ulceration is considerable: 32% of patients are depressed and this is associated with a three-fold greater risk of mortality [5]. In 2010-11 the NHS spent approximately £650 million on diabetic foot care: equivalent to £1 in every £150 of NHS spending [6].

Despite the fact that diabetic foot care has been identified as a priority by the National Institute for Health and Care Excellence (NICE), the NHS and Diabetes UK [4,7,8], there is currently a lack of evidence-based treatments which prevent ulceration. NICE guidance for ulcer prevention in diabetic patients with a history of ulceration focuses on risk assessment in primary care; referral to foot protection teams and 'basic foot care education' (undefined). For active ulceration, the guidance is rapid referral to multidisciplinary foot care teams [4]. However, successive systematic reviews have found no evidence that education alone improves clinical outcomes [9-15]. NICE have consequently called for further research in this area and the development of new interventions targeting psychological and behavioural factors, which research suggests may play a central role in the healing and prevention of foot ulcers [16,17].

A complex intervention [17] has previously been developed in accordance with the MRC's guidance on complex interventions [18]. This intervention aimed to (i) reduce re-ulceration risk by modifying associated psychological and behavioural factors and (ii) improve ulcer healing in the event of re-ulceration, by encouraging rapid self-referral and effective self-management. This intervention originally consisted of two phases conducted face-to-face over five months: an initiation phase of ten weekly sessions, which established the foundations for psychological and behavioural change, and a maintenance phase involving two additional sessions held one and three months later, which encouraged the patient to sustain the changes made in the initiation phase.

The intervention was tested in a small feasibility RCT (n=15) which: (i) established the feasibility of training nurses and podiatrists to deliver the intervention; (ii) established that patients would consent to participate in an RCT; and (iii) that the intervention is acceptable (no withdrawals post randomisation and all participants attended at least 80% of sessions). Refinements to the content of the intervention also indicated that the components of the initiation phase of the intervention could be delivered in eight, rather than 10, weekly sessions. Qualitative research with patients suggested that that the intervention seemed to modify the psychological and behavioural precursors of reulceration risk and ulcer healing; with changes sustained for eight months. However, feedback from participants indicated that support for long-term change may be more effective if available indefinitely, and as and when patients require it.

In follow up work [19] the investigators have examined the acceptability and feasibility of providing this long-term support through a digital platform. People with a history of prior ulceration reported that a digital solution would be acceptable, but that an alternative (i.e., a written handbook) should

also be available. Also, within this work, the first phase of developing this digital intervention was completed, in accordance with the Person Based Approach (PBA) to intervention development [20]. This involved identifying the key issues that need to be addressed in the intervention:

- Managing difficult feelings.
- Promoting and sustaining moderate and stable levels of activity.
- Promoting and sustaining regular and effective checking of feet for early signs of ulceration.
- Facilitating rapid self-referral in the event of changes in foot health.

Theoretical modelling of the intervention has also been completed to identify the key determinants of the above areas of psychological and behavioural functioning and these have been mapped on to the behaviour change wheel to identify appropriate theory-based behaviour change techniques [21].

1.1. The Revised REDUCE Intervention

Thus, the revised REDUCE intervention consists of an eight week initiation phase delivered weekly (in sessions of approximately 60 minutes), with access to a web-based digital package which will provide long-term support for the psychological and behavioural changes achieved in the initiation phase. The *behavioural goals/outcomes* are to improve foot-checking, physical activity and encourage rapid self-referral (in the event of changes in foot health); and, in so doing, increase ulcerfree days. We hypothesise that the mechanisms (our 'mechanisms of change') by which REDUCE will achieve these goals, will be improved mood, reduced social isolation, development of new foot-care behaviours and changes in illness beliefs. The delivery of the intervention will be carried out remotely by HCPs trained in the REDUCE intervention in accordance with routine NHS processes. Sites are currently engaged in remote delivery of many aspects of patient care, therefore the delivery of the intervention remotely is now more likely to be familiar and acceptable to participants.

The first ('Initiation') phase of REDUCE starts the process of modifying these 'mechanisms of change'. This will be achieved through a suite of intervention techniques delivered in eight weekly face-to-face sessions. Comparable techniques will be utilised in the second ('Maintenance') phase although with a focus on sustaining change, delivered via a digital platform (and handbook).

Thus, the two phases of REDUCE are intended to flow together but with a slightly different emphasis in their intervention techniques given their respective focus on the initiation, versus maintenance, of behaviours. For example, the 'Initiation' phase will provide detailed information about the benefits of making behaviour changes (e.g., to avoid future ill-health) and will aim to increase perceptions of risk, whilst supporting self-efficacy. It will also provide guidance and support on how to perform key behaviours (e.g., foot checking, activity scheduling for behavioural activation). In contrast, the 'Maintenance' phase will provide only brief guidance on how to perform these behaviours, in order to serve as reminders and reinforce messages from the 'Initiation' phase. Similarly, the 'Maintenance' phase will include brief reminders about the benefits of behaviour change to reinforce messages about risk, and thus support motivation.

The 'Initiation' phase will also seek to modify illness beliefs (e.g., positive outcome expectations, self-efficacy, perceived control over illness), mood, key behaviours and social isolation through the use of

Cognitive Behavioural Therapy (CBT) techniques (positive reframing, behavioural experiments, behavioural activation). In contrast, the 'Maintenance' phase will provide resources to facilitate the continued use of these techniques (e.g., thought diaries, spaces to reflect on behavioural experiments, diaries for activity scheduling). Both phases will also use self-monitoring, with feedback on progress with goals/action plans. In the 'Initiation' phase the feedback will include Socratic questioning if the participant is facing barriers to behaviour change. This is a well-established therapeutic approach which involves the use of probing questions which encourage the treatment recipient to become aware of and reflect on their reasons for engaging in specific behaviours. This in turn enables them to develop appropriate solutions. Within the 'Maintenance' phase the participant will ask themselves Socratic questions when reviewing goals/action plans.

The delivery of the 'Initiation' sessions will be structured as follows:

- Assessment of current difficulties;
- Identify problematic behavioural, cognitive and emotional responses;
- Socialisation to the therapeutic model;
- Explore the role of thoughts and behaviours and their link with mood and/or health status;
- Negotiate individualised goals, a stepped approach 'homework';
- Increasing awareness of activity patterns and behaviours which impact on ulcer outcomes;
- Negotiating appropriate behaviours;
- Increasing awareness and exploring of unhelpful cognitions (e.g., hopelessness);
- Identifying sources of social support;
- Discussing how to be more assertive/test out with behavioural experiments;
- Taking responsibility, strengthening commitment to new behaviours and planning for the future.

The 'Maintenance' phase will be delivered on a digital platform and through a handbook and focuses on supporting four key areas of psychological and behavioural functioning:

- · Managing difficult feelings.
- Promoting and sustaining moderate and stable levels of activity.
- Promoting and sustaining regular and effective checking of feet for early signs of ulceration.
- Facilitating rapid self-referral in the event of changes in foot health.

1.2. Development of REDUCE Maintenance Intervention

Prior to this study, the *think aloud* methodology has been used to obtain feedback from our PPI members to explore their perceptions of the maintenance intervention to ensure the content was as acceptable, feasible, persuasive and motivating as possible. The feedback has been used to update the maintenance intervention for the pilot trial.

1.3. Pilot Trial

An external pilot trial will be completed to examine recruitment and retention rates and inform estimates regarding the number of recruiting centres and the recruitment period required for the clinical and cost-effectiveness trial. We will also examine the viability of primary and secondary outcome data collection. The design of this pilot will therefore mirror the main features of the clinical and cost-effectiveness trial.

As findings could result in changes to the intervention, the training programme, and/or the study design and processes, an external, rather than internal, pilot is most appropriate. However, should findings from this pilot not result in significant changes to REDUCE or the REDUCE training programme, we would consider treating this pilot trial as an internal pilot, with patient and HCP data contributing to the main trial and the process evaluation.

1.3.1. Health Economic Evaluation

The pilot trial will assess the feasibility of collecting the economic outcomes in preparation for the main trial, drawing upon our findings from previous work including the perspectives of commissioners and service providers and as noted in 1.2 Development of REDUCE Maintenance Intervention. We will pilot the methods to collect resource use data from patient-level questionnaires and other data collection sources (e.g. primary, community and secondary patient medical records). We will also consider what are the most relevant and important drivers of health and social care costs (and additionally, costs to patients and society) so that these can be accurately collected within the main trial. Finally, we will also consider what are the key drivers of resource use and costs associated with the REDUCE intervention, with appropriate face validity checks, to ensure we have understood and accounted for the treatment pathways of both arms.

2. OBJECTIVES

2.1. Primary Objectives

The primary objectives of this pilot trial are to investigate the following prior to conducting a larger clinical and cost-effectiveness trial:

- 1. Feasibility of the recruitment strategy for participants, to include numbers of eligible patients approached; numbers not eligible (and why); and proportion of eligible patients consented.
- 2. Adherence to and attrition from the REDUCE intervention and to the trial (to include reasons for attrition and how this is documented).
- 3. Feasibility of obtaining outcome data from primary, community and secondary care patient medical records. Completeness of data collection.
- 4. Feasibility of collecting the planned economic outcome measures. Completeness of data collected.
- 5. Identify whether adaptations are required to the REDUCE intervention.
- 6. Test out and refine data collection methods for the mixed-methods process evaluation to be undertaken in the main trial.
- 7. Determine if refinements are required to the intervention fidelity tool.
- 8. Determine if modifications are needed prior to the clinical and cost-effectiveness trial to:
 - a. the REDUCE intervention and/or training programme;
 - b. the logic model.

3. STUDY DESIGN

A multi-centre, parallel group, randomised controlled external pilot trial with nested qualitative study.

4. STUDY SETTING

This is a multi-centre randomised controlled pilot trial involving at least two clinical sites recruiting 15-20 participants (i.e., 7-10 participants per site). It is anticipated that the participant population will be recruited from specialist multidisciplinary diabetic foot clinics at participating secondary care NHS Trusts. The intervention will be undertaken at the participating Trusts.

Usual care for both arms of the study will be provided by the clinical care teams in primary care, secondary care and community health including community podiatry teams.

Clinical outcome data will be extracted from any relevant healthcare records including (but not limited to) primary care, secondary care, community health and podiatry records.

5. ELIGIBILITY CRITERIA

5.1. Participant Inclusion Criteria

We will include adults who fulfil all of the following inclusion criteria:

- Has diabetes [according to World Health Organization (WHO) criteria].
- Is aged 18 years or over.
- Has two lower limbs (i.e. has not had major amputation of either lower limb).
- Has a recently healed diabetic foot ulcer (if more than one, all must be healed), defined as fully epithelialised with no drainage, for a minimum two weeks.
- Has cognitive capacity to provide informed consent, to engage with the study intervention (both as digital and written handbook versions), to take part in interviews if randomised to the intervention, and to provide follow-up data.
- Has sufficient command of English language to engage with the intervention and to provide follow-up data.

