5.2. Participant Exclusion Criteria

We will exclude all adults who meet any of the following exclusion criteria:

- Has active Charcot Neuro-osteoarthropathy.
- Presence of active diabetic foot ulceration.
- Diagnosis of a current severe mental illness which could hinder engagement with the trial and/or intervention (e.g., psychosis).
- Has previously been randomised to this pilot trial.
- Is currently taking part in another study which would affect the outcomes of this study (e.g. diabetic foot ulcer wound healing medicinal product trial or other behavioural intervention study).

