6. PROCEDURES

6.1. Recruitment

6.1.1. Participant Identification

6.1.1.1 Pilot Trial Participants

Over a three-month recruitment period potential participants will be identified from and screened by their clinical care team in specialist multidisciplinary diabetes foot clinics at the participating NHS Trusts. Medical records will be accessed only by a member of the existing clinical care team (not by the research team) in order to establish whether they are eligible to be invited to take part in the study. No details about patients will be passed on to the research team at this stage.

Potential participants on clinical caseloads will be screened against the eligibility criteria in the pilot trial sites. Those eligible will be approached about the trial by their usual clinical carers and given some details about the study, including an information sheet. Participants will be provided with information regarding the trial as soon as possible after healing of all their foot ulcers, but will only be recruited and consented at a separate clinic visit after the ulcer has remained healed for a period of at least two weeks (i.e., clinical definition of healing).

It will be clearly stated that the potential participant is free to withdraw from the study at any time for any reason without prejudice to future care, and with no obligation to give a reason for withdrawal. Should new information arise during the study, which may affect a participant's willingness to take part, this will be reviewed for addition to the participant information sheet and a revised consent form will be completed as necessary.

The potential participant will be allowed as much time as they wish to consider the information, and will be given the opportunity to question the Principal Investigator, the research team, their GP or other independent parties to decide whether they will participate in the study.

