6.6. Data Collection

6.6.1. Clinical Team Completed Case Report Forms (CRFs)

Case report forms will be used to collect the following clinical and demographic data:

- Screening:
 - Inclusion and exclusion criteria;
- Baseline:
 - o Participant contact details name, address, telephone number and email address
 - Demographics (date of birth) and NHS number;
 - Previous medical history duration (years) and type of diabetes, most recent HbA1c value if available, depression, documented peripheral neuropathy, documented peripheral arterial disease (PAD), visual impairment, other relevant conditions;
 - Diabetic foot ulcer (DFU) history single ulcer versus multiple ulcers, most recent episode confirmed healing date, activity/education/footwear;
- Clinical outcomes (via notes review by blinded outcome assessors)
 - Ulcer-free days;
 - Days to re-ulceration (if re-ulceration occurs);
 - Number of ulcers;
 - Days in hospital;
 - AEs;
 - SAEs;
 - Amputations major and minor;
 - Mortality;

Resource use data.

The clinician baseline CRF will be completed on paper, a copy will of the completed CRF will be securely stored in the site ISF and the original CRF will be posted to YTU.

Healthcare professionals who are not involved in delivering the REDUCE intervention, the research outcome assessors (nurses or practitioners), will support the collection of Clinical Outcome data at three months post randomisation. Data will be collected from relevant health care records, to include but not limited to, secondary care, GP, community health and community podiatry records. Paper forms will be provided, a copy will of the completed CRF will be securely stored in the site ISF and the original CRF will be posted to YTU.

Intervention session details will be collected and will include:

- Session number;
- Date:
- Attendance:
- Session delivered by;
- Length of session;
- Interventions/modalities delivered;
- Completion of home practice.

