9. STATISTICS AND HEALTH ECONOMICS

9.1. Sample Size Calculation

This study is an external pilot RCT and as a result the sample size has not been calculated to assess the effectiveness of the intervention. We will enlist two sites to recruit 15-20 participants over a three month period. This would mean a recruitment yield of approximately four participants per site per month, which is comparable to the yield we would require in a main trial, and will provide an opportunity to determine whether recruitment estimates need to be refined. In addition, this sample size, together with a 2:1 allocation ratio, will provide a sufficient number of intervention participants for the qualitative study.

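### The three-month recruitment count can mix a one-off backlog of already healed patients with a continuing flow, so projecting its crude monthly rate over a longer main-trial window can overstate recruitment.

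*Protocol*

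**What the plan says.** **Eligibility.** Inclusion (5.1) requires a recently healed ulcer, with all ulcers healed if there was more than one. The definition given is "fully epithelialised with no drainage, for a minimum two weeks". The Study Summary repeats it: "recently healed DFU (fully epithelialised with no drainage, for a minimum two weeks". Among the exclusions (5.2), the entry on ulcer status is "Presence of active diabetic foot ulceration"; none concerns how long ago healing took place.

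**Screening.** Section 6.1.1.1 sets a three-month recruitment period and states "Potential participants on clinical caseloads will be screened against the eligibility criteria in the pilot trial sites". It also says "Participants will be provided with information regarding the trial as soon as possible after healing of all their foot ulcers", with consent at a separate clinic visit once the ulcer has stayed healed for at least two weeks.

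**Use of the count.** Section 9.1 plans 15-20 participants from two sites in three months, a yield it puts at about four per site per month, "which is comparable to the yield we would require in a main trial". Section 1.3 says the pilot will "inform estimates regarding the number of recruiting centres and the recruitment period required for the clinical and cost-effectiveness trial". Section 9.2 makes the number recruited the primary stop-go criterion.

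**Data and summaries.** The baseline CRF (6.6.1) records the "most recent episode confirmed healing date". Section 9.4 summarises numbers screened, eligible, consenting and randomised. It does not mention splitting recruits by healing date or calendar month.

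**The concern.** A definition with only a lower bound, applied to a standing caseload, admits two kinds of recruit. Some had already passed the two-week mark when the site opened; they form a stock that can be drawn on once. Others pass it during the window; they arrive at a rate that continues. A three-month count adds the two together.

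For a pilot of the same length as the main trial's recruitment this would not matter, because the mix would be the same. It matters when a rate from a short window is carried to a longer one, since the stock does not renew. The number of sites and the recruitment period for the main trial are the planning quantities this pilot is meant to inform. An overstated sustained rate would lead to too few sites or too short a period.

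**Working it through.** **1. The plan's own figure.** Sites (2), months (3) and target (15-20) come from 9.1. Crude yield = N / (sites × months):

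- 15 / (2 × 3) = 2.50 per site per month
- 20 / (2 × 3) = 3.33 per site per month

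The stated figure of about four is not reproduced; four per site per month would give 4 × 2 × 3 = 24 recruits. That is a separate matter, and nothing below depends on it.

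**2. Splitting the count.** Let c be the crude monthly rate per site and f the share of the three-month count that was already eligible at opening. The documents do not give f, so it is an assumption here. Per site:

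- backlog B = 3cf, available once
- continuing rate r = c(1 − f)

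Continuing rates per site per month:

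| | f = 0 | f = 25% | f = 50% |
|---|---|---|---|
| N = 15 | 2.50 | 1.88 | 1.25 |
| N = 20 | 3.33 | 2.50 | 1.67 |

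**3. Projecting to a main-trial window of T months per site.** Main-trial sites also open with a backlog. Assuming it is the same size as at the pilot sites, a site recruits B + rT = c[3f + T(1 − f)]. The crude projection is cT. The overstatement factor is therefore

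T / [3f + T(1 − f)],

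which does not depend on N.

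| Window T | f = 0 | f = 10% | f = 25% | f = 50% |
|---|---|---|---|---|
| 3 months | 1.00 | 1.00 | 1.00 | 1.00 |
| 6 months | 1.00 | 1.05 | 1.14 | 1.33 |
| 12 months | 1.00 | 1.08 | 1.23 | 1.60 |
| Long-run limit, 1/(1 − f) | 1.00 | 1.11 | 1.33 | 2.00 |

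Example with 10 recruits per site and f = 50%: backlog 5, continuing rate 5/3 = 1.67 per month. Twelve months gives 5 + 20 = 25, against 40 from the crude rate; 40/25 = 1.60. With f = 25%: 2.5 + 2.5 × 12 = 32.5, and 40/32.5 = 1.23. The 6- and 12-month windows are also assumptions, since the protocol does not state the main trial's recruitment period.

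**4. What f = 25-50% would mean.** Suppose healing and consent rates are constant, nobody re-ulcerates, and sites reach patients healed up to L months before opening. Those healed between half a month and L months earlier form the backlog, so f = (L − 0.5)/(3 + L − 0.5), and L = 0.5 + 3f/(1 − f). This gives L = 1.5 months at f = 25% and 3.5 months at f = 50%. A look-back of one month gives f = 0.5/3.5 = 14%. The assumed range is possible under the eligibility wording, but nothing in the protocol shows that it would occur.

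**5. Precision.** If recruits arrive as a Poisson count, the relative standard error of a rate is 1/√n: about 26% for 15 recruits and 22% for 20. At f = 50% of 15, about 7.5 recruits remain in the continuing group, with 1/√7.5 = 37%. The last month alone would hold about 15/3 = 5 to 20/3 = 6.7 recruits over both sites.

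**The case against.** Section 6.1.1.1 describes an approach made soon after healing, which reads like a prospective flow. Recruitment is in specialist multidisciplinary foot clinics, and section 1 describes those teams as the referral route for active ulceration, with foot protection teams for people with a past ulcer. Long-healed patients may therefore be few on these caseloads. This stands as a reason why f may be small. It does not make f zero: the timing of the approach does not restrict who is eligible, and the same section screens existing caseloads.

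The recruitment findings are said only to inform estimates, and no extrapolation formula is fixed. The detailed tables may be in the statistical analysis plan, which is not at hand. This stands too: the lack of a table in the protocol is not in itself an error. What the protocol does fix is the open-ended definition, the screening of caseloads and the use of recruitment for main-trial planning, and these together create the mixture.

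A reader might infer that the main trial will need 1.33 to 2 times the site-months that the crude rate implies. The documents do not support this. That figure gives main-trial sites no opening backlog of their own, and it rests on an assumed share that leaves out zero.

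A reader might also infer that the stop-go decision should rest on the newly eligible recruits or on the final month. With about 5 to 7 recruits in that month, and few in a subset, such a rule would be too imprecise and could wrongly fail a feasible trial.

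**Conclusion.** The point holds as a possibility that the plan could measure cheaply, not as a demonstrated bias. The direction follows from the text: any backlog makes the crude three-month rate too high for a window longer than three months. The size cannot be determined from the protocol. With no backlog there is none; with an assumed 25-50% backlog, the crude projection is too high by a factor of about 1.14-1.33 over 6 months and 1.23-1.60 over 12 months. These figures assume the same backlog per main-trial site as in the pilot and a constant continuing rate.

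Neither the eligibility criterion nor the stop-go count is shown to be wrong. This is an inexpensive improvement to how the recruitment result is carried into main-trial planning.

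**What to change.** Leave the eligibility criteria and the stop-go count unchanged. In 9.4:

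- Use the healing date on the baseline CRF to classify each recruit by whether two weeks healed was first reached before, or on or after, the opening of that site. A cut at the healing date itself would misplace patients healed less than two weeks before opening. It would also leave the newly healed group only about 2.5 of the 3 months in which to be recruited.
- State whether the recorded date is the day of healing or the day two weeks of healing was confirmed, since 6.1.1.1 treats the two-week period as the clinical definition of healing.
- Report recruits per site and month for each group, with time since healing.
- Project main-trial sites and duration as a one-off opening backlog per site plus the continuing monthly rate. Show the combined rate alongside, and state the imprecision that comes with 15-20 recruits.

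The cost is one small table and no new data item for recruits. The downside is that the projected yield may look less favourable.
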